## Appendix XVII

### Medication - Overuse Headache Criteria (MOH)

From International Headache Society ICHD-3 Classification  
([8.2 Medication-overuse headache \(MOH\) - ICHD-3](#) Accessed April 12, 2022)

#### 8.2 Medication-overuse headache (MOH)

**Previously used terms:**

Drug-induced headache; medication-misuse headache; rebound headache.

**Coded elsewhere:**

Patients with a pre-existing primary headache who, in association with medication overuse, develop a new type of headache or a significant worsening of their pre-existing headache that, in either case, meets the criteria for 8.2 *Medication-overuse headache* (or one of its subtypes) should be given both this diagnosis and the diagnosis of the pre-existing headache. Patients who meet criteria for both 1.3 *Chronic migraine* and 8.2 *Medication-overuse headache* should be given both diagnoses.

**Description:**

Headache occurring on 15 or more days/month in a patient with a pre-existing primary headache and developing as a consequence of regular overuse of acute or symptomatic headache medication (on 10 or more or 15 or more days/month, depending on the medication) for more than 3 months. It usually, but not invariably, resolves after the overuse is stopped.

**Diagnostic criteria:**

- A. Headache occurring on  $\geq 15$  days/month in a patient with a pre-existing headache disorder
- B. Regular overuse for  $> 3$  months of one or more drugs that can be taken for acute and/or symptomatic treatment of headache
- C. Not better accounted for by another ICHD-3 diagnosis.

**Notes:**

1. Patients should be coded for one or more subtypes of 8.2 *Medication-overuse headache* according to the specific medication(s) overused and the criteria for each below. For example, a patient who fulfils the criteria for 8.2.2 *Triptan-overuse headache* and the criteria for one of the subforms of 8.2.3 *Non-opioid analgesic-overuse headache* should receive both these codes. The exception occurs when patients overuse combination-analgesic medications, who are coded 8.2.5 *Combination-analgesic-overuse headache* and not according to each constituent of the combination-analgesic medication.
2. Patients who use multiple drugs for acute or symptomatic treatment of headache may do so in a manner that constitutes overuse even though no individual drug or class of drug is overused; such patients should be coded 8.2.6 *Medication-overuse headache attributed to multiple drug classes not individually overused*.
3. Patients who are clearly overusing multiple drugs for acute or symptomatic treatment of headache but cannot give an adequate account of their names and/or quantities are coded 8.2.7 *Medication-overuse headache attributed to unspecified or unverified overuse of*

*multiple drug classes* until better information is available. In almost all cases, this necessitates diary follow-up.

**Comments:**

8.2 *Medication-overuse headache* is an interaction between a therapeutic agent used excessively and a susceptible patient. Among those with a previous primary headache diagnosis, most have 1. *Migraine* or 2. *Tension-type headache* (or both); only a small minority have other primary headache disorders such as 3.3 *Chronic cluster headache* or 4.10 *New daily persistent headache*.

The diagnosis of 8.2 *Medication-overuse headache* is extremely important clinically. Epidemiological evidence from many countries indicates that more than half of people with headache on 15 or more days/month have 8.2 *Medication-overuse headache*. Clinical evidence shows that the majority of patients with this disorder improve after discontinuation of the overused medication, as does their responsiveness to preventative treatment. Simple advice on the causes and consequences of 8.2 *Medication-overuse headache* is an essential part of its management and can be provided with success in primary care. An explanatory brochure is often all that is necessary to prevent or discontinue medication overuse. Prevention is especially important in patients prone to frequent headache.

The behaviour of some patients with 8.2 *Medication-overuse headache* is similar to that seen with other drug addictions, and the Severity of Dependence Scale (SDS) score is a significant predictor of medication overuse among headache patients.

In the criteria below for the various subtypes, the specified numbers of days of medication use considered to constitute overuse are based on expert opinion rather than on formal evidence.

It is recognized that cross-sectional population-based studies estimating the prevalence of 8.2 *Medication-overuse headache* can record the coexistence in participants of headache on  $\geq 15$  days/month and overuse of drugs for acute and/or symptomatic treatment of headache but are rarely able to collect information on earlier headache, on duration of the current headache or medication overuse, and/or that might support a presumption of causation. In consequence, either or both of criteria A and B may not be entirely fulfilled. Provided that criteria are not fulfilled for another ICHD-3 diagnosis, such cases should be reported as *probable medication-overuse headache* (pMOH), although ICHD-3 does not provide a coding for this

Primary Objective 
• To explore the effectiveness of eptinezumab on patient-centered outcomes	Exploratory Endpoints 
1. Good Day/Bad Day scale at weeks 4, 12, and 242. Euroqol 5 Dimension – 5 Levels (EQ-5D-5L) at weeks 4, 12, and 243. Patient-Identified Most Bothersome Symptom (PI-MBS) at weeks 4, 12, and 244. Healthcare resource utilization (HCRU) at weeks 4, 12, 245. Headache Impact Test – 6 (HIT-6) change from baseline at week 4, 12, and 246. Migraine Disability Assessment (MIDAS) change from baseline at week 12 and 247. Treatment Satisfaction Questionnaire for Medication (TSQM) at week 248. Medication Switching at week 12 and 249. Shared Decision-Making Questionnaire-9 (SDMQ-9) at screening and week 2410. SURE test at screening11. Patient Activation Measure – 10 (PAM-10) at screening, week 12 and 2412. Infusion Satisfaction Survey (ISS) at baseline and at week 12
Safety objective 
• To evaluate the safety and tolerability of eptinezumab	Safety endpoints 
• Reported adverse effects

2 Study Design

This is an exploratory, prospective, randomized, pragmatic, open-label cohort study of 200 participants receiving preventive treatment for episodic migraine (EM) or chronic migraine (CM) headache in the United States (US). Participants must have a history of ≥ 8 migraine days in two of the past three months prior to enrolment and have documented failure to at least two previous oral preventive treatments per the American Headache Society (AHS) Consensus Statement.

Panel 2 Criteria for Chronic Migraine Diagnosis per International Headache Society (IHS) International Classification of Headache Disorders 3rd edition (ICHD-3).

[figure not shown]
1.1 Migraine Without Aura	1.2 Migraine With Aura
A. At least five attacks fulfilling criteria B-D	A. At least two attacks fulfilling criteria B and C
B. Headache attacks lasting 4-72 hours when untreated or unsuccessfully treated.	B. One or more of the following fully reversible aura symptoms:
C. Headache has at least two of the following four characteristics:	1. visual 2. sensory 3. speech and/or language 4. motor 5. brainstem 6. retinal
1. unilateral location 2. pulsating quality 3. moderate or severe pain intensity 4. aggravation by or causing avoidance of routine physical activity (e.g. walking or climbing stairs)	C. At least three of the following six characteristics:
D. During headache, at least one of the following:	1. at least one aura symptom spreads gradually over ≥ 5 minutes 2. two or more aura symptoms occur in succession 3. each individual aura symptom lasts 5-60 minutes 4. at least one aura symptom is unilateral 5. at least one aura symptom is positive 6. the aura is accompanied, or followed within 60 minutes, by headache
1. nausea and / or vomiting 2. photophobia and phonophobia	D. Not better accounted for by another ICHD-3 diagnosis
E. Not better accounted for by another ICHD-3 diagnosis	
1.3 Chronic Migraine	

A. Headache (migraine-like or tension-type-like) on ≥ 15 days/month for > 3 months, and fulfilling criteria B and C.
 
B. Occurring in a patient who has had at least five attacks fulfilling criteria B-D for 1.1 Migraine Without Aura and/or criteria B and C for 1.2 Migraine With Aura
 
C. On ≥ 8 days/month for > 3 months, fulfilling any of the following:
 
 1. criteria C and D for 1.1 Migraine Without Aura 2. criteria B and C for 1.2 Migraine With Aura 3. believed by the patient to be migraine at onset and relieved by a triptan or ergot derivative 
D. Not better accounted for by another ICHD-3 diagnosis
	

This study will be conducted in compliance with the protocol, *Good Clinical Practice* and applicable regulatory requirements.

Participants will be recruited from sites that can administer all therapies within the study in an outpatient setting.

After giving consent, participants will be classified as living with either EM or CM per International Classification of Headache Disorders 3rd edition (ICHD-3) guidelines (see [Panel 2](#)) based upon their medical history. Within these strata, the participants living with EM will be randomized to eptinezumab or subcutaneous (SC) anti-calcitonin gene-related peptide (aCGRP) (i.e., erenumab, fremanezumab or galcanezumab) in a 1:1 manner. Those experiencing CM will be randomized to eptinezumab, SC CGRP, or Botox in 3:2:1 manner. Participants randomized to the SC CGRP injectable arm will be free to select treatment with any aCGRP injectable of their choice (i.e., erenumab, fremanezumab or galcanezumab). Please see [Panel 3](#) for further details on the randomization design.

Panel 3 Randomization Design

Participants will be followed prospectively for 24 weeks; a follow-up phone call will then be made to each participant 8 weeks after study completion at the End of Treatment/Early Termination Visit. At Screening, all participants will be trained to use an eDiary (a smartphone application) that will prompt participants to report their headache status on a daily basis, any related symptoms and any use of acute migraine medications. In addition, the eDiary will also prompt participants three times each week to report any interactions with the healthcare system (e.g., office visits, emergency room visits/urgent care visits, hospitalizations, prescription medication, etc.). The site staff will also follow-up with participants at each study visit to record additional details of healthcare resource utilization (HCRU) recorded in the eDiary, record HCRU not reported in the eDiary, and record reasons for any changes in prescription or over-the-counter (OTC) medications. Quality of life (QOL) data and HCRU data will be collected from participants via the smartphone application (app) and from the site staff via electronic data capture (EDC). QOL assessments include the EQ-5D-5L, HIT-6, Good Day/Bad Day scale, and MIDAS. Participants will complete the EQ-5D-5L and Good Day/Bad Day scale on a weekly basis, the HIT-6 monthly, and the MIDAS every 3 months via the eDiary.

Participant preferences in making a treatment selection will be measured using the SDM-Q-9 (at Screening and Week 24). Participant confidence in the treatment selection they made will be measured via the SURE test (at the Screening Visit only). Participants' knowledge, skill and confidence in managing their own health will be assessed at screening, week 12 and week 24 via the PAM-10 instrument. Participants' satisfaction with their treatment experience will be assessed at week 24 via the TSQM. The SDM-Q-9, SURE test, PAM, and TSQM will be completed electronically.

For participants on eptinezumab, satisfaction with their infusion experience will be assessed via the Infusion Satisfaction Survey after each infusion (at Visit 2 and Visit 5) using a paper questionnaire.

2.1 Rationale for the Study Design

EVEC is an exploratory, prospective, randomized, pragmatic, open-label study. This design allows for the collection of real-world data to better understand how eptinezumab compares to other advanced preventives for prevention of migraines.

2.2 Study design justification

Justification for two treatment groups

Eptinezumab is the fifth treatment option made available to people living with migraine for prevention of migraine attacks. As such the decision that insurers and prescribers must make is, “What benefit does this new treatment create over those options currently available?” Payers must consider whether to add eptinezumab to their formulary. Thus, whether eptinezumab improves efficacy over the basket of available treatments is the key question, rather than whether it is superior to a single treatment.

Justification for 6-month observation period

It is known that patients experience an early onset of efficacy with eptinezumab, and pooled analyses with other advanced preventives indicate that this early onset provides a comparative advantage to eptinezumab. However, less is known regarding the sustainability of this advantage. The durability of effect is a key element in the decision making of payers, thus 6-months is considered the minimum relevant period of observation.

Justification for an open-label study

EVEC is intended to be a real-world evidence study to answer the question for patients, prescribers and payers seeking to know the comparative effectiveness of eptinezumab in actual clinical practice. In the real-world, patients and their professional caregivers (physicians and staff) know what medication the patient receives; therefore, the same principle applies here. In addition, masking participants to treatment assignment in this study would require that every participant receive at least two of the following: 1) monthly sham injection; 2) 30 in-office sham injections in their head and face quarterly; or 3) a quarterly sham infusion. While this may reflect an internally valid study design, it is far from a real-world clinical experience.

Justification for use of an active comparator/no placebo

As noted above, this is a real-world study to evaluate the comparative effectiveness of eptinezumab against other advanced preventives for migraine. The justification for

comparison to a “market basket” of current treatments is noted above in the “Justification for two treatment groups.” We note here that we consider only an active comparator and no placebo because in a real-world setting no patient would receive a placebo. So only active comparators are considered.

3 Definitions

3.1 Definition of Periods

The study will have four periods:

- Screening (Visit #1) to Baseline (Visit #2)

At screening participants will complete the informed consent, review the patient decision aid describing the treatments, complete the SDMQ-9, SURE test, PAM-10, and receive training in use of the study eDiary app. During the period from Screening to Baseline, the participant will use the study app to report their daily experience. This will capture their compliance behavior to support the study analysis while also giving the participant training in use of the app. The site investigator will receive the treatment allocation and receive the participant’s first dose.

- Baseline to Week 12 (Visit #5)

During this period, participants will complete the daily diary, and the weekly and monthly patient-reported outcomes (PROs) as prompted by the study app. This period is the primary reporting period for the study. Participants randomized to receive eptinezumab or onabotulinumtoxinA will receive that treatment at Visit #5 at the study site. Those randomized to receive a subcutaneously injected aCGRP may visit the study site at Visit #5 for the follow-up visit or visit the study site.

- Baseline to Week 24 (Visit #8)

For reporting purposes, the period for visits 6-8 will be pooled with the previous period, so that results for week #24 will include all data since the Baseline visit. From the patient perspective there is no change in the required behavior.

- Safety Follow-up period (Week 25-33, Visit #9)

This is the two-month follow-up period required by Lundbeck to assess safety.

The reporting schedule is defined in the table that follows:

Panel 4 Patient Reported Outcomes Reporting Schedule

Assessments	Reporting Schedule				
	Daily	Weekly ^(a)	Monthly ^(b)	Quarterly ^(c)	Early Termination
Healthcare Resource Utilization	X ^(d)				X
EQ-5D-5L		X			X
Good Day/Bad Day Scale		X			X
PSS			X		X
HIT-6			X		X
PAM-10				X	X
MIDAS				X	X
SDM-Q-9				X	X
TSQM				X ^(e)	X

(a) Weekly = every 7 days, Visit 2 date = Day 0

(b) Monthly = every 28 days, Visit 2 date = Day 0

(c) Quarterly = every 84 days, Visit 2 date = Day 0

(d) Will be assessed 3 times per week

(e) Assessed at Day 168 only

Participants will report daily whether they have had a headache in the previous 24 hours, any migraine related symptoms (concurrent with the migraine or interictal) and use of rescue medication.

3.2 Definition of Baseline

The screening assessment (Visit 1) is to be conducted within 14 days of the participant's initial treatment at the Baseline Visit (Visit 2) to allow the investigator sufficient time to review the participant's medical history and determine if the participant is eligible for study participation.

The participant's first treatment occurs as the Baseline Visit. The day of the visit, the participant will be notified by the study app to complete the Baseline PROs and prior to initiating treatment the site will confirm the completion. The participant will also complete the Daily Headache Status Report in their eDiary on this date. Administration of the first treatment will consist of either the participant's first treatment with eptinezumab or Botox or the participant's first injection of a subcutaneous aCGRP mAb. For participants in the subcutaneous aCGRP arm, the first dose should be self-administered by the participant under the supervision of the site staff.

Where a study endpoint is based upon the change from baseline, the report at this visit will serve as that baseline.

3.3 Definition of Withdrawal

Withdrawal from the study is defined as termination of consent on or before Visit 8. Participants who withdraw from the study prior to Visit 8 will be asked to complete an Early Termination Visit. The visit must be scheduled as soon as possible after withdrawal. All information collected at an Early Termination Visit is to be recorded in the Visit 8 forms of the electronic case report form (eCRF). If the patient denies completing the Early Termination Visit, then no further data will be collected.

No participant will be withdrawn from the study due to non-compliance with treatment. As this is a pragmatic real-world study, the failure to comply with treatment is considered a real-world outcome. However, an investigator may withdraw a participant from the study based upon their medical judgement if they deem continued involvement in the study is detrimental to the participant's welfare.

No new information will be collected from participants who withdraw from the study, except information collected in relation to the scheduled Withdrawal Visit or needed for the follow-up of adverse events.

The reason for withdrawal must be recorded in the eCRF.

For a participant who withdraws consent:

- If the participant withdraws consent during a visit and then agrees to it being the final visit, the investigator will complete the visit as a Withdrawal Visit and all the data collected up to and including that visit will be used
- If the participant withdraws consent during a telephone conversation, the investigator will ask the participant if they might attend a Withdrawal Visit. If the participant:
 - Agrees to attend a Withdrawal Visit, all the data collected up to and including that visit will be used
 - Refuses to attend an Early Termination Visit, the investigator should attempt to follow the participant's safety and future treatment; any information collected will only be recorded in the patient's medical records

If the participant explicitly requests that their data collected from the time of withdrawal of consent onwards not be used, this will be respected.

The end of the study for an individual participant is defined as the last protocol-specified contact with that patient. The overall end of the study is defined as the last protocol-specified contact with the last patient ongoing in the study.

3.4 Definition of Planned versus Actual Treatment

As this is a pragmatic real-world study, there is no restriction on treatment pathways following randomization with the exceptions defined below. Note that all participants will be analyzed on an "intention to treat" basis, regardless of changes made to their treatment following the Baseline visit.

Participants may switch to an alternative preventive treatment in either treatment cohort after they have received their initial treatment with the medication to which they were randomized. Such a decision may be made upon recommendation of their treating clinician or participant preference. The site staff will investigate the reason for treatment change with both the treating clinician and participant. The use of medications, including gepants, for relief of acute migraine symptoms in either treatment arm is permitted and will be recorded in the smartphone application.

For all participants, the treatment to which they are initially assigned must be the treatment given at Baseline (Visit 2). Switching of medication is not permitted prior to administration of the first dose of medication. For participants who receive eptinezumab or Botox as their initial treatment and elect to switch to a subcutaneous aCGRP injectable (i.e., erenumab, fremanezumab or galcanezumab), they may not do so until week 12 (visit 5). Participants who receive eptinezumab or Botox at week 12 (Visit 5) will not be permitted to switch their treatment for the remaining duration of the study.

Participants initially treated with a subcutaneous aCGRP injectable may only switch to eptinezumab, or Botox at week 12 (visit 5) due to the design of the study. However, these participants may switch to another of the subcutaneous aCGRP injectable medications at any time, once the treatment window for their previous injection has ended.

No changes in treatment will be permitted after Visit 7.

All changes in treatment are to be documented in the eCRF.

If a participant wishes to switch their medication but does not meet the specified criteria to do so, as stated above, they should be withdrawn from the study and be treated as per standard of care by their physician.

3.5 Definition of Migraine and Headache Days

3.5.1 Headache Day

A headache day will be defined as a day in which the participant reports the following:

- Reported “yes” to having a headache in the past 24 hours and who do NOT report criterion A nor B:
 - o Criterion A
 - Headache with ≥ 2 of the following features:
 - Moderate or severe pain intensity
 - Unilateral location
 - Pulsating quality
 - Aggravation by or causing avoidance of routine physical activity
 - During the headache, the patient reports ≥ 1 of the following symptoms:
 - Nausea and/or vomiting

- Photophobia
- Phonophobia
- Criterion B
 - Reported acute medication use

3.5.2 Migraine Day

A migraine day will be defined as a day in which a patient reports the following features consistent with ICHD-3 criteria for migraine without aura ([Panel 2](#)):

- Reported “yes” to having a headache in the past 24 hours and who also report either criterion A or B:
 - Criterion A
 - Headache with ≥ 2 of the following features:
 - Moderate or severe pain intensity
 - Unilateral location
 - Pulsating quality
 - Aggravation by or causing avoidance of routine physical activity
 - During the headache, the patient reports ≥ 1 of the following symptoms:
 - Nausea and/or vomiting
 - Photophobia and
 - Phonophobia
 - Criterion B
 - Reported acute medication use

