#### 9.1.1 Diagnostic Assessments

IHS ICHD-3 guidelines sections 1.1, 1.2 and 1.3 for Migraine or Chronic Migraine are the diagnostic criteria to be used when assessing participant eligibility (see [Table 1](#)). Fulfilment of criteria for EM or CM according to the inclusion criteria in this protocol will be confirmed by the investigator from the participant's medical record.

A migraine day for both chronic and episodic migraine is defined as any day with a headache that meets the chronic migraine definition as outlined in the IHS guidelines (section 1.3.1.1) for controlled trials of preventive treatment of chronic migraine in adults. This is defined as a day with a headache that lasts at least 4 hours; meets ICHD-3 criteria C and D for migraine without aura (1.1), B and C for migraine with aura (1.2), or ICHD-3 criteria for probable migraine (1.5); or a day with a headache of a minimum 30-minute duration that is successfully treated with a triptan, ergotamine, or other migraine-specific acute medication.

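### SAP 3.5.2 counts any headache with any acute medication as a migraine day, an undeclared departure from Protocol 9.1.1, and criterion A differs between SAP 3.5.1 and 3.5.2

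*SAP*

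**What the plan says.** SAP 3.5.2 classes a day as a migraine day if the participant answers yes "to having a headache in the past 24 hours and who also report either criterion A or B". Criterion A combines at least two of four pain features with at least one associated symptom. Criterion B reads, in full, "Reported acute medication use". The section introduces the rule as one in which the patient "reports the following features consistent with ICHD-3 criteria for migraine without aura", with a pointer to SAP Panel 2.

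Protocol 9.1.1 gives two routes. The first is a headache of at least 4 hours that meets the ICHD-3 features of migraine without aura, migraine with aura, or probable migraine. The second is "a day with a headache of a minimum 30-minute duration that is successfully treated with a triptan, ergotamine, or other migraine-specific acute medication".

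SAP 3.5.1 defines a headache day as a reported headache in participants "who do NOT report criterion A nor B". Its criterion A lists photophobia and phonophobia as two separate items. In 3.5.2 the corresponding line is printed "Photophobia and", followed by phonophobia. Panel 2 prints the pair as one item, "photophobia and phonophobia".

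SAP section 17, on changes from the protocol's analyses, is marked not applicable.

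**The concern.** There are two separate problems.

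First, criterion B has none of the protocol's three conditions on a treated headache: drug class, treatment success and minimum duration. Under it, the migraine-day count is partly a record of medication-taking. The SAP analyses migraine medication separately as healthcare resource use (11.2.2, 18.6.2), so the two quantities overlap by construction. Protocol 5.4 admits participants with chronic migraine and medication overuse, including overuse of combination analgesics, so treated headaches that would not meet the protocol's drug route are plausible in this population.

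Second, a headache day is meant to be a headache that is not a migraine day. That works only if both sections use the same criterion A. As printed they do not, and some reported headaches are left without a class.

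At stake is the meaning of the migraine-day variable wherever it is used, and whether a report can say that it follows the protocol's definition.

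**Working it through.** The plan states no figure on this point, so there is none to reproduce. The check compares the rules and then counts the answer patterns.

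**1. Protocol and SAP side by side.** The last column gives the effect of each SAP departure with everything else held fixed.

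| Element | Protocol 9.1.1 | SAP 3.5.2 | Effect on the count |
|---|---|---|---|
| Symptom route: duration | at least 4 hours | none | can only add days |
| Symptom route: headache types | without aura, with aura, probable migraine | without-aura features only | can only remove days |
| Drug route: drug | migraine-specific | any acute drug | can only add days |
| Drug route: result | successful | not required | can only add days |
| Drug route: duration | at least 30 minutes | none | can only add days |

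One departure lowers the count and the others raise it. The documents give no frequencies for any of them and do not print the probable-migraine criteria, so the sign of the net difference cannot be derived.

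**2. What counts as acute medication.** The eDiary (Protocol Panel 3) asks which medication was taken to relieve the headache, without limiting the class. SAP 18.6.2 lists non-narcotic and anti-inflammatory analgesics and antiemetics as acute drugs, alongside triptans and ergots. Criterion B therefore takes in simple analgesics. The without-aura criteria in Panel 2, to which 3.5.2 points, have no medication-only route.

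**3. Do the SAP's classes cover every reported headache?** Take a day with a headache and eight yes/no answers: four pain features, nausea or vomiting, photophobia, phonophobia, and acute medication. That gives 2^8 = 256 patterns, 128 with medication and 128 without. Read the split line in 3.5.2 as the joint item in Panel 2.

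- At least two of four pain features: 6 + 4 + 1 = 11 of 16 combinations.
- Symptom part of criterion A, out of 8 combinations: 3.5.2 is met by 4 (nausea or vomiting) + 1 (both sensitivities without it) = 5. 3.5.1 is met by 8 − 1 = 7.
- With medication: all 128 are migraine days through criterion B. Of these, 11 × 5 = 55 also meet criterion A, so 128 − 55 = 73 qualify through B alone. One of the 73 has no pain feature and no associated symptom.
- Without medication: 11 × 5 = 55 are migraine days and 128 − 11 × 7 = 51 are headache days. The remaining 128 − 55 − 51 = 22 are neither.
- Total migraine-day patterns: 128 + 55 = 183. No pattern is in both classes.

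The 22 are untreated headaches with at least two pain features, no nausea or vomiting, and exactly one of photophobia and phonophobia (11 × 2 = 22). They cannot be clear days under SAP 3.5.3, because a headache was reported.

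If 3.5.2 instead meant three separate items, the untreated migraine-day patterns become 11 × 7 = 77 and the gap closes (128 − 77 − 51 = 0). The rule then departs from the Panel 2 criterion to which it points. An edit is needed on either reading.

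**4. Where the variable is used.** Diary migraine days enter the weekly derivation (SAP 18.15.1), the supplementary Spearman correlations (11.2.7), the regression in 15.1, and the protocol's objective on monthly migraine days as a mediating factor (Protocol section 2).

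**The case against.** The strongest reply is that this is a loose definition of a variable that is not an endpoint. Monthly migraine days was removed as an outcome and is absent from SAP Panel 1. The 11.2.7 analysis is supplementary and uses the whole cohort, not an arm comparison. The SAP has no mediation model. The regression in 15.1 is said to test the primary hypothesis, but it sits in a section offered as illustration, and 11.2.2 contains no migraine-day model. All of this stands, and it limits the consequence.

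It can be added that rank correlations are unaffected by uniform proportional over-counting. That is true, but criterion B does not act uniformly: it adds days according to how often each person treats a headache, so ranks can change.

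The photophobia mismatch may be a line-break slip. That is likely, and the effect is small: no analysis in section 11 uses the 3.5.1 headache day, and an unclassified day still enters the 18.15.1 proration as a reported day without migraine. The text still needs one reading.

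Two stronger inferences are tempting. A reader might conclude that on-study migraine days are inflated relative to the protocol, perhaps by a stated percentage. The documents do not support that, because the SAP also drops the aura and probable-migraine routes, and any percentage would only restate assumed headache frequencies. A reader might also conclude that the SAP rule spoils a comparison with baseline. Baseline migraine days come from screening history confirmed with the treating physician, so they differ in source from diary counts under any definition. No analysis of change from baseline in migraine days is planned.

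**Conclusion.** The concern holds in limited form. As written, SAP 3.5.2 departs from Protocol 9.1.1 in both its drug route and its symptom routes without declaring it, and the headache-day and migraine-day rules do not fit together. Criterion B on its own can only add days, and it makes the count partly a measure of medication use. The net direction against the protocol's definition is undetermined, and no percentage should be attached to it.

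The sizes that can be given are pattern counts: 73 of 183 migraine-day patterns qualify through criterion B alone, and 22 of 256 patterns have no class. They rest on reading 3.5.2's split line as Panel 2's joint item, and they say nothing about how often such days occur. No listed endpoint is affected. The definitions should be corrected, because the uses in step 4 otherwise rest on a variable that does not follow the protocol.

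**What to change.** - **Criterion B:** restrict it in both 3.5.1 and 3.5.2 to migraine-specific acute drugs rated effective by the participant. The eDiary already collects the drug taken and its effectiveness (Protocol Panel 3). The SAP should list the qualifying drugs and the rating that counts as success. Restricting drug class alone would not reproduce the protocol's route.
- **Criterion A:** use one identical text in 3.5.1 and 3.5.2, with photophobia and phonophobia as a single joint item as in Panel 2, so that every reported headache falls in exactly one class.
- **Missing routes:** add the protocol's aura and probable-migraine routes as far as the diary symptoms allow.
- **Section 17:** declare and justify whatever still differs. Duration is the likely case: Protocol Panel 3 lists no headache-duration item, so the 4-hour and 30-minute limits may not be derivable.

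The cost is SAP text and derivation programming. No new data collection is needed.
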